##### Time to recovery

Time to recovery is calculated as:

date of first time WHO scale score  $\leq 3$  - study drug administration date; or date of discharge from hospital - study drug administration date, whichever occurs first.

In the case that a patient does not reach WHO scale score  $\leq 3$  criteria, the patient will be censored at EOS visit.

Additionally, time to recovery will be analyzed using an adapted derivation:

date of first time WHO scale score  $\leq 3$  – randomization date or date of discharge from hospital  $\leq 3$  – randomization date, whichever occurs first. Related output will be noted as sensitivity analysis.

Time to recovery will be analyzed based on mITT and EE Set. Sensitivity analysis for time to recovery will be analyzed based on mITT only.

Time to recovery with WHO scale score  $\leq 3$  without supplemental oxygen

Some patients were discharged from hospital while still using supplemental oxygen and so an additional sensitivity analysis will be performed to evaluate the impact for time to recovery. The following Pseudo-Code will be applied in the given order to derive time to recovery without supplemental oxygen:

1. Derive time to event 'T' as date of first time WHO scale score  $\leq 3$  - study drug administration date; or date of discharge from hospital - study drug administration date, whichever occurs first.
2. For subjects who discharged earlier than reporting an WHO scale score  $\leq 3$  apply the following checks:
  - a. If an supplemental oxygen dose of '0' is reported at day of discharge keep T.
  - b. If an supplemental oxygen dose of '0' is already reported one day prior day of discharge use T-1.
  - c. If an supplemental oxygen dose of  $>0$  is reported at day of discharge and discharge reason indicate that the subject is not on oxygen (e.g. "On Room Air" or "Weaned off O2") keep T.
  - d. If an WHO scale score  $\geq 4$  is reported at day of discharge and an WHO scale score  $\leq 3$  is reported one day after discharge use T+1.
  - e. If an WHO scale score  $\geq 4$  is reported at day of discharge and an WHO scale score  $\leq 3$  is reported two days after discharge use T+2.
  - f. If an WHO scale score  $\geq 4$  is reported at day of discharge and none of the criteria above are met use T+2.
3. In the case that a patient does not reach WHO scale score  $\leq 3$  criteria or has no discharge event, the patient will be censored at EOS visit.

Time to recovery with WHO Scale score  $\leq 3$  and without supplemental oxygen will be analyzed based on mITT and EE Set.

*Proportion of patients achieving recovery by Day 14 and by Day 28*

Number and percentage of patients achieving recovery (WHO scale score  $\leq 3$  or discharge from hospital, whichever occurs first) by Day 14 and by Day 28 will be presented.

*Duration of supplemental oxygen (O2) requirement :*

The number of days with supplemental oxygen (O2) will be calculated as:

stop date of supplemental oxygen – start date of supplemental oxygen +1; if supplemental oxygen started after study drug administration; otherwise supplemental oxygen – date of study drug administration +1.

If there are multiple periods of supplemental oxygen (O2), total days will be the sum of each period. Patients who die or withdraw from the study with ongoing supplemental oxygen at the last contact date, days will be (earliest of [date of death, EOS date] – start date of supplemental oxygen +1). Standard descriptive statistics (mean, SD, median, minimum, maximum) will be used. Standard descriptive statistics will also be presented for mITT Set excluding withdrawals and deaths.

Days of supplemental oxygen (O2) up to Day 14 will be used as a sensitivity analysis. Days will be calculated as below:

- For patients who Die or Withdraw before Day 14, their total will be factored-up to an equivalent 14 day period. For example, if a patient withdraws on Day 5 having already received 3 days of supplemental oxygen between Day 1 and Day 5, then their endpoint value will be 8.4 days i.e.  $(3/5)*14$  .
- For patients who do not withdraw or die before Day 14, count the actual days on supplemental oxygen (O2) up to Day 14.

*Number of days with fever (temperature  $>100.4^{\circ}\text{F}$  [ $38.0^{\circ}\text{C}$ ]):*

The Number of days with fever are calculated as:

stop date of fever – start date of fever +1, if fever started after study drug administration; otherwise stop date of fever – date of study drug administration +1.

If there are multiple periods of fever, Total days will be the sum of each period. Standard descriptive statistics (mean, SD, median, minimum, maximum) will be used. Standard descriptive statistics will also be presented for mITT Set excluding withdrawals and deaths.

Days with fever up to Day 14 will be used as a sensitivity analysis. Days will be calculated the same as described for Days of supplemental oxygen (O2) up to Day 14.

Change from baseline in WHO Ordinal Scale score

The description of the WHO Ordinal Scale score is shown in [Section 6.2](#). The Number and percentage of patients on WHO Scale scores and change from baseline (-7, -6, -5, -4, -3, -1, 0, 1, 2, 3, 4) will be presented by visit. Shift table will be presented by visit as well.

Simple Ordinal logistic regression on the WHO Scale score at each visit (Days 5, 7, 14, 28, and 60) will be performed to compare ATYR1923 1 mg/kg versus Placebo and ATYR1923 3 mg/kg versus Placebo. Firth logistic regression ([Firth, 1993](#)) on the collapsed WHO Ordinal Scale (0-3 versus 4-8) at each visit (Days 5, 7, 14, 28, and 60) will be performed as well.

Distribution of WHO Ordinal Scale at 1, 2, 3, 4, 5, 6, 7, 10, 14, 28 and 60 days will be visualized by treatment group using an stacked bar chart. These figures will only consider scheduled assessments and in case the scheduled assessment is not available the mapped unscheduled TC follow up assessments as defined in [Section 4.2](#).

Time to Improvement in Clinical Status

Time to improvement in days is the time in which the patient sees a decrease after study treatment in the WHO Ordinal Scale score from baseline by at least 1 point, derived as:

date of decrease in WHO scale compared to baseline by at least 1 point - study drug administration date; or date of discharge from hospital - study drug administration date, whichever occurs first.

In the case that a patient has not decreased in the WHO scale or withdraws from the study, they will be censored at EOS date. Time to improvement will be analyzed using the Kaplan-Meier methods and Cox Proportional Hazards model as described in the above.

Repeat analysis above for improvement of WHO Ordinal Scale score by at least 2 points.

Additionally, time to improvement will be analyzed using an adapted derivation: date of decrease in WHO scale compared to baseline by at least 1 point - randomization date; or date of discharge from hospital - randomization date, whichever occurs first.

Related output will be noted as sensitivity analysis.

Time to improvement (by at least 1 and 2 points) will be analyzed based on mITT and EE Set. Sensitivity analysis for time to improvement will be analyzed based on mITT only.

*All-cause mortality*

Number and percentage of patients who died will be summarized by day 14, 28 and 60 by treatment group. If the total number  $\leq 3$ , only listing will be presented.

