5.1. Inclusion Criteria

The following inclusion criteria must be met for a patient to be eligible for inclusion in the study:

1. Age 18 to 75 years.
2. Confirmation of SARS-CoV2 infection by PCR.
3. Severe pneumonia related to SARS-CoV2 infection, defined as fever or suspected respiratory infection with radiographic abnormalities suggestive of viral pneumonia, plus at least one of the following:
 - Respiratory rate >30 breaths/min; or
 - Severe respiratory distress, as determined by the Investigator; or;
 - Oxygen saturation (SpO_2) $\leq 93\%$ on room air.
4. Female patients of childbearing potential must be willing to use adequate contraception from Screening until 30 days after the last follow-up visit. Male patients, if not infertile or surgically sterilized, must agree to use adequate contraception and not donate sperm from Day -1 until 30 days after the last follow-up visit. (Refer to [Section 7.1.6.2](#) for details regarding adequate contraception.)
5. Signed informed consent by patient or designated representative.

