14. APPENDICES

Appendix 1: WHO Ordinal Scale for Clinical Improvement

Patient State	Descriptor	Score
Uninfected	No clinical or virological evidence of infection	0
Ambulatory	No limitation of activities	1
	Limitation of activities	2
Hospitalized Mild disease	Hospitalized, no oxygen therapy	3
	Oxygen by mask or nasal prongs	4
Hospitalized Severe Disease	Non-invasive ventilation or high-flow oxygen	5
	Intubation and mechanical ventilation	6
	Ventilation + additional organ support – pressors, RRT, ECMO	7
Dead	Death	8

Source: WHO R&D Blueprint novel Coronavirus, COVID-19 Therapeutic Trial Synopsis.
Available at: https://www.who.int/blueprint/priority-diseases/key-action/COVID-19_Treatment_Trial_Design_Master_ProtocolSynopsis_Final_18022020.pdf

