#### 4.7 Demographic and Other Baseline Characteristics

Demographic and other baseline characteristics will be summarized by treatment group, for both treatment groups combined (Total) and All Patients using the mITT set. The summaries provided will include the following:

- Demographic variables:
  - Age (continuous and categorical [ $<65$  years;  $\geq 65$  years]),
  - Sex,
  - Race,
  - Ethnicity,
  - Baseline height,
  - Baseline weight,
  - Baseline Body Mass Index (BMI) continuous and categorized ( $<30$ ,  $\geq 30$ ) and ( $<35$ ,  $\geq 35$ ).

Age will be calculated based on date of randomization. BMI will be calculated based on baseline height and weight as weight (kg) / height (m^2).

- Baseline disease characteristics:
  - Baseline WHO Ordinal Scale,
  - Baseline maximum temperature measurements,
  - Baseline oxygen utilization (yes, no), if yes method of Oxygen delivery,
  - Baseline oxygen saturation  $\leq 86\%$ ,
  - Days since onset of COVID-19 related symptoms,
  - Days hospitalized prior Day 1.

Technical Note: Onset of COVID-19 related symptoms are documented on the Medical History Form. Use the earliest MH record related to COVID-19 and derive as: date of study drug administration – date of start of first MH record related to COVID-19.

- Risk Factors at Baseline:
  - subjects with Age  $\geq 65$  years,
  - subjects with Obesity (BMI  $\geq 30$ ),

---

- subjects with Morbid Obesity (BMI  $\geq 35$ ),
- subjects with Diabetes (MH PT: type 2 diabetes mellitus, diabetes mellitus),
- subjects with Hypertension (MH PT: hypertension),
- subjects with Coronary Artery Disease (MH PT: coronary artery disease),
- subjects with Chronic Kidney Disease (MH PT: chronic kidney disease),
- subjects with Chronic Respiratory Disease (MH PT: Asthma; Chronic obstructive pulmonary disease; Sleep apnoea syndrome),
- subjects with Cardiovascular Disease (MH SOC: Cardiac Disorders),
- subjects with 1, 2, 3, 4, 5, 6, or 7 risk factors present at baseline.

**Technical Note:** Medical History Terms that are related to COVID-19 will not be considered for risk factors. The risk BMI  $\geq 30$  and/or  $\geq 35$  will be counted as only one risk factor per subject and further, risk of coronary artery disease and/or cardiovascular disease will only be counted as one risk factor per subject.

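### The recovery endpoint has no rule for a patient who enters at WHO score 3: such a patient counts as recovered at time zero or earlier, whatever happens later

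*SAP*

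**What the plan says.** **Entry.** Protocol 5.1, criterion 3, asks for fever or suspected respiratory infection with suggestive imaging, plus one of three findings: "Respiratory rate >30 breaths/min; or" "Severe respiratory distress, as determined by the Investigator", or a room-air saturation of 93% or lower. The exclusions in Protocol 5.2 remove intubated or ventilated patients and set no lower bound on the WHO score.

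**Scale.** In Protocol Appendix 1, score 3 is "Hospitalized, no oxygen therapy".

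**Endpoint.** SAP 4.9.4.1 takes the "date of first time WHO scale score" of 3 or less minus the dosing date, or discharge minus dosing, whichever is first. Step 1 of the oxygen-free recovery pseudo-code repeats this. The SAP also asks for the "Number and percentage of patients achieving recovery (WHO scale score" of 3 or less, or discharge) by Day 14 and by Day 28.

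**Related text.** SAP 4.7 tabulates "Baseline oxygen utilization (yes, no), if yes method of Oxygen delivery". For time to improvement, SAP 4.9.4.1 requires the decrease to come after study treatment. Time to recovery has no such condition.

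**The concern.** A patient who enters at score 3 already meets the definition of recovery, so the endpoint records a success without any change in the patient's condition. Because only the first qualifying score counts, a later rise to 4 or more, intubation or death does not undo it.

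A second route does not need a baseline of 3. A patient scored 3 during Screening and 4 at the last pre-dose assessment would, on a literal reading, also be timed as recovered before dosing.

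The stakes are the Cox hazard ratio, the early Kaplan-Meier estimates (SAP 4.9.4 reports them from Day 5), the Day 14 and Day 28 proportions, and the subgroup repeats. Arms have about 10 patients, so each such patient is 10 percentage points of an arm. Neither document describes stratification by baseline score.

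**Working it through.** The documents give no event rate, effect size or power for this endpoint, so there is no figure to reproduce. The check covers logic, dates and size.

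**1. Can a patient enter at score 3?** Yes. Each of the three severity findings can be met by a patient who is not receiving oxygen, and no other criterion sets a minimum score.

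**2. What time does the formula give?** T = date of first score of 3 or less − dosing date. SAP 4.2 has no Day 0.

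| First score of 3 or less | T from dosing | T from randomization, if one day before dosing |
|---|---|---|
| Day −7 | −7 | −6 |
| Day −3 | −3 | −2 |
| Day −1 | −1 | 0 |
| Day 1 | 0 | 1 |

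Negative values need a Screening score. Protocol Table 1 and SAP 3.2 (Table 1) place the first WHO score at Screening. The schedule in SAP Appendix 6.1, as extracted, starts on Day 1 pre-dose, which gives 0. SAP 4.2 and 4.9.4.1 have no rule for T of zero or less. The negative-time rule in SAP 4.3.2 concerns imputed days for death and hospitalization dates.

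**3. Would a post-dose condition be enough?** No. A patient who stays at 3 would get T = 0 if scored after dosing on Day 1 (Protocol Table 1), or T = 1 if next scored on Day 2 (SAP Appendix 6.1). The condition removes negative times and the Screening-only route, but baseline-3 patients still count as early recoveries.

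**4. Size with no drug effect.** Assumptions: 10 patients per arm (30 randomized 1:1:1), k baseline-3 patients in one arm and none in the other, and a constant recovery hazard h among the rest. The documents give no value for h, so I use 0.05, 0.13 and 0.25 per day.

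Shift in recovery by day t, in points = 10 × k × exp(−h × t).

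| h per day | Day 5, k = 1 / 2 / 3 | Day 14, k = 1 / 2 / 3 | Day 28, k = 1 / 2 / 3 |
|---|---|---|---|
| 0.05 | 7.8 / 15.6 / 23.4 | 5.0 / 9.9 / 14.9 | 2.5 / 4.9 / 7.4 |
| 0.13 | 5.2 / 10.4 / 15.7 | 1.6 / 3.2 / 4.9 | 0.3 / 0.5 / 0.8 |
| 0.25 | 2.9 / 5.7 / 8.6 | 0.3 / 0.6 / 0.9 | below 0.1 |

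For the hazard ratio I simulated 3,000 trials per setting, with T = 0 for baseline-3 patients, times in whole days and censoring at Day 60. Across the three hazards the median hazard ratio was 0.98-1.01 for k = 0, 1.12-1.14 for k = 1, 1.24-1.25 for k = 2 and 1.39-1.41 for k = 3. Separate simulations at 0.13 per day gave up to 1.14, 1.28 and 1.43. Rounded, that is about 1.1, 1.3 and 1.4. With k = 0, the central 95% of hazard ratios already ran from about 0.4 to 2.7.

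**5. Dilution if the drug works.** Assume recovery of 50% against 80% among the other patients, and k baseline-3 patients in each arm. Difference = (1 − k/10) × 30 points: 30, 27, 24 and 21 points for k = 0, 1, 2 and 3.

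**The case against.** The strongest reply is that the problem may never arise. No document shows a patient with baseline score 3. A reader might infer from the yes/no oxygen row in SAP 4.7 that the SAP expects patients without oxygen, but a table category does not predict that anyone will fall into it. Protocol 8.3.3 provides for saturation measured on oxygen when a room-air reading is not feasible, so patients already on oxygen are plainly foreseen. The change-from-baseline categories in SAP 4.9.4.1 stop at +4, whereas death from score 3 would be +5, which hints that the authors assumed a baseline of 4 or more. That hint is weak, since the same list omits −2, and it is not an eligibility rule.

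A post-dose reading is also the likely intent. SAP 4.9.4 counts Kaplan-Meier days from dosing, and time to improvement is explicitly post-treatment.

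Much would be visible anyway. Baseline WHO score is tabulated by arm, shift tables would show a 3-to-3 patient, and time to discharge does not use the threshold. The subgroup split at 5 does not isolate score 3.

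The endpoints are exploratory, without multiplicity adjustment (SAP 4.9.2), and the primary endpoint is safety. The shifts are small beside the sampling noise in arms of 10.

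All of this limits the size of the point. It does not supply the missing rule: if such a patient exists, the formula as written gives a wrong event time and a wrong recovery status.

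**Conclusion.** The gap is real and conditional. Eligibility admits score 3, score 3 satisfies recovery, and neither document has a rule for that patient. T is 0 on the dosing-date formula, and negative only if a Screening score is used. It can be +1 in the randomization-date sensitivity analysis.

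A reader might infer that the recovery results are biased in favour of ATYR1923. The documents do not support that. Randomization makes either arm equally likely to receive such patients, so the effect is chance imbalance, plus dilution of any true difference.

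The hazard-ratio shifts of about 1.1, 1.3 and 1.4 rest on one-sided placement of 1, 2 or 3 patients in arms of 10, and vary little with the assumed hazard. The shift in proportions does depend on it: about 3-8, 6-16 or 9-23 points at Day 5. At 0.13 per day it falls to about 2 to 5 points at Day 14 and under 1 point at Day 28. At 0.05 per day it is still 5 to 15 points at Day 14. The actual number of such patients is unknown and may be zero. The primary safety endpoint is unaffected.

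**What to change.** In SAP 4.9.4.1, define recovery as the first post-dose WHO score of 3 or less, or discharge, whichever is first. Apply this to the main and randomization-date derivations, step 1 of the oxygen-free pseudo-code, the Day 14 and Day 28 proportions, and the subgroup repeats in SAP 4.9.4.2.1.

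Keep the mITT analysis. Beside it, add a labelled analysis of time to recovery and the Day 14 and Day 28 proportions restricted to patients with baseline WHO score 4 or more, using the SAP 4.2 definition of baseline. List patients with baseline 3 or less by arm. Both parts are needed, because the post-dose condition alone leaves these patients as recoveries at T = 0 or 1.

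Dropping these patients from the mITT analysis is not advisable. Recovery is a protocol-defined secondary endpoint, and the SAP revision history shows changes to a recovery analysis after unblinding. Any change made after database lock should be labelled post hoc, as SAP 3.2 requires, and reported beside the definition now in the SAP.

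The cost is a little extra analysis and a slightly smaller set in the restricted analysis. If no patient had a baseline score of 3 or less, one sentence saying so replaces the restricted analysis.

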8.3. Efficacy and Exploratory Assessments

8.3.1. Hospitalization Status

The date, time and reason of initial hospitalization and discharge are to be documented in the eCRF. During hospitalization, the date and time of any change in the patient's hospitalization status, specifically admittance and discharge to the intensive care unit are also to be recorded. If, in the Investigator's opinion, the patient required a higher level of care (ie, admittance to the intensive care unit) but did not receive due to resource availability, this should be documented.

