### 4.2 General Presentation Considerations

**Baseline:** the last available pre-treatment assessment, unless otherwise specify. All assessments should have time collected. If time is not collected and date of assessment is the same as study drug administration date then assessment will be assumed to be collected prior to treatment unless schedule of assessments and protocol indicate planned collection is always after dosing.

For baseline of oxygen use, total oxygen use in 24 hours before drug administration date.

**Day-of-Discharge (DoD):** day when patient is discharged from the hospital.

**Date of discharge:** date patient is discharged from the hospital.

**Early Termination (ET):** day when patient withdraws from the study before completion.

**End-of-Study (EOS):** the EOS assessment is at Day 60 for patients who complete the study.

**End of study date:** date of EOS assessment (Day 60) if patient completes the study or date of early withdrawal if patient discontinues early, or date of death.

**Study Day:** <Assessment Date> - study drug administration date + 1 if <Assessment Date> is on or after study drug administration date. <Assessment Date> - study drug administration date, if <Assessment Date> is before study drug administration date.

Durations are generally calculated as the stop date - start date +1, if not otherwise stated.

For elapsed time (eg, time since the initial diagnosis) is calculated as reference date - event date.

If more than one laboratory value is available for a given study day, the last valid observation will be used in summaries, unless otherwise stated. If it is not possible to determine which is the last measurement due to missing times, then the average of all measurements for that study day will be used as the value for that study day. All observations will be presented in listings.

Laboratory data will be presented in standard units.

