#### 4.9.4.1 Secondary Efficacy Analyses

##### Time to hospital discharge

Time to hospital discharge will be calculated as:

discharge date – study drug administration date.

Patients who die in hospital will be censored at death date. Patients still in hospital at EOS will be censored at EOS visit.

For imputation of partial missing dates for death or discharge from hospitalization see [Section 4.3.2](#).

Additionally, time to hospital discharge will be analyzed using an adapted derivation: discharge date – randomization date. The same rules for handling of hospitalized or discontinued patients and partial missing data applies as mentioned above. Related output will be noted as sensitivity analysis.

Time to hospital discharge will be analyzed based on mITT and EE Set. Sensitivity analysis for time to hospital discharge will be analyzed based on mITT only.

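### Any hospital discharge, whatever its reason, counts as recovery and as improvement, although the protocol defines recovery by WHO score alone

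*SAP*

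**What the plan says.** **Recovery.** SAP 4.9.4.1 (Time to recovery) takes the earlier of the first WHO score ≤3 and "date of discharge from hospital - study drug administration date, whichever occurs first". The recovery proportions use the same composite: "or discharge from hospital, whichever occurs first) by Day 14 and by Day 28 will be presented".

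**Improvement.** SAP 4.9.4.1 (Time to Improvement in Clinical Status) counts a drop of at least 1 point from baseline, "or date of discharge from hospital - study drug administration date, whichever occurs first". It then adds: "Repeat analysis above for improvement of WHO Ordinal Scale score by at least 2 points".

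**Discharge.** SAP 4.2 defines the date of discharge only as "date patient is discharged from the hospital". It does not mention reason, destination or oxygen status.

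**Discharge reason.** Protocol 8.3.1 requires it: "The date, time and reason of initial hospitalization and discharge are to be documented in the eCRF". The SAP uses it analytically in one place, step 2c of the oxygen-free sensitivity analysis, where the event time is kept if the "discharge reason indicate that the subject is not on oxygen".

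**Protocol definition.** Protocol 3.2 and the endpoint list in SAP 3.4.2 define recovery as WHO ≤3 and do not mention discharge. SAP Table 1 (changes to planned analyses) lists only the new starting point for time to improvement.

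**Time to hospital discharge.** This endpoint has its own non-event rule: "Patients who die in hospital will be censored at death date. Patients still in hospital at EOS will be censored at EOS visit".

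**The concern.** Discharge is a fair stand-in for recovery when a patient goes home better. It is a poor one when the patient leaves for end-of-life care, leaves against advice, or moves to another hospital and the move is recorded as a discharge. Nothing in the event rule separates these cases. A patient on high-flow oxygen (WHO 5) who went to hospice on Day 10 and died on Day 12 would, on the event definition, be recovered and improved by both 1 and 2 points on Day 10.

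The outputs affected are time to recovery, recovery by Day 14 and Day 28, and time to 1-point and to 2-point improvement. The rule also carries into the versions timed from randomization and the recovery subgroup analyses. If such departures differed by arm, the hazard ratios and proportions would favour the arm with more of them. In a trial of 30 patients, a single case is visible.

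**Working it through.** The plan gives no power, event-rate or effect figure for these endpoints (SAP 3.1.4), so there is nothing to reproduce. The check has two parts: reading the rules together, and measuring the leverage of one patient.

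**1. How the rules treat a patient discharged at WHO ≥4 with no later score ≤3**

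| Rule | Result |
|---|---|
| Time to recovery, event definition | Recovered on the discharge date |
| Time to recovery, censoring sentence (WHO ≤3 not reached) | Censored at EOS |
| Recovery by Day 14 / Day 28 | Recovered if discharged by then |
| Time to improvement, event definition | Improved on the discharge date, for 1 and 2 points |
| Time to improvement, censoring sentence (no decrease in score, or withdrawal) | Censored at EOS date |
| Oxygen-free sensitivity analysis, step 2f | Recovered at T+2 |

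The event definitions and censoring sentences give opposite answers. Step 2f shows which way the SAP leans: where no earlier criterion applies, discharge at WHO ≥4 delays the event by two days but does not remove it.

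**2. Effect of one patient on the proportions**

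Inputs: 30 patients randomized 1:1:1 (SAP 3.1.4), so 10 per arm and 20 in ATYR1923 Total. SAP 4.3.1 keeps every patient in the denominator.

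- One arm: 1/10 = 10 percentage points; two patients, 2/10 = 20.
- ATYR1923 Total: 1/20 = 5 percentage points.

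Illustration with assumed counts and the continuity-corrected Wilson interval named in SAP 4.9.4:

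- One arm: 8/10 = 80% (95% CI 44.2 to 96.5) becomes 7/10 = 70% (35.4 to 91.9).
- ATYR1923 Total: 16/20 = 80% (55.7 to 93.4) becomes 15/20 = 75% (50.6 to 90.4).

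**3. Chance that at least one such discharge occurs**

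The documents give no rate. For an assumed rate p, the chance of at least one among 30 is 1 − (1 − p)^30:

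| Assumed p | 1% | 3% | 5% | 10% |
|---|---|---|---|---|
| Chance of at least one | 26% | 60% | 79% | 96% |

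**4. Effect of one patient on the hazard ratio**

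These data are invented, with times in days from dosing. Placebo: events at 5, 6, 7, 7, 8, 10, 12, 15, and two patients censored at 60. Active: events at 4, 5, 5, 6, 6, 7, 9, 11, 14, and one censored at 60. One of the two active patients with time 5 is taken to have left without recovering. Cox model, Efron ties:

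| Scoring of that patient | HR (95% CI) | Active recovered by 14 days |
|---|---|---|
| Event at T = 5 (event definition) | 1.64 (0.63 to 4.27) | 9/10 |
| Event at T+2 = 7 (step 2f) | 1.57 (0.60 to 4.09) | 9/10 |
| Not recovered, at risk to 60 | 1.18 (0.44 to 3.14) | 8/10 |

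In this example the T+2 rule removes little of the effect. The intervals are wide under every scoring.

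**The case against.** **Discharge fits the scale.** In the WHO scale appended to both documents, living patients outside hospital score 0 to 2. An ordinary discharge from WHO 4 or 5 is therefore a real fall of at least 2 points. This stands: the rule is a reasonable proxy and fails only in particular cases.

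**The cases are hypothetical.** Neither document mentions hospice, departure against advice or transfer. Exclusion criterion 2 removes patients whose death is judged imminent. The discharge problem that the SAP does name is leaving while still on oxygen. This stands: a reader might infer that such patients occurred or that results are biased, and the documents do not show either.

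**The text is not unequivocal.** The censoring sentences could be read as protecting against the problem, and a patient who leaves and withdraws could be censored at withdrawal. Nothing says that an inter-hospital transfer is recorded as a discharge. This stands as a limit. But wording that contradicts the event definition is an ambiguity to resolve, not a safeguard.

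**Time to hospital discharge.** A reader might extend the criticism to this endpoint. The documents do not support that: Protocol 3.2 names it as time to discharge, and counting discharges is what it measures.

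**Other outputs would show the cases.** The by-visit WHO regressions use the recorded score, and all-cause mortality would capture a death after discharge. The EE Set allows exclusions. The first two help interpretation but leave the recovery and improvement results unchanged. The EE Set was added after unblinding, rests on sponsor judgement, has no discharge rule and does not alter the mITT analysis.

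**These endpoints are exploratory.** True. SAP 4.9.2 treats all p-values that way, and the primary endpoint (TEAEs) is untouched.

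**Conclusion.** The concern holds for the recovery and improvement endpoints. As defined, discharge alone is sufficient for success whatever its reason. That criterion goes beyond the protocol's definition of recovery, is not listed among the SAP's changes, and conflicts with the SAP's own censoring sentences. The oxygen-free sensitivity analysis does not close the gap.

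Each affected patient moves an arm's recovery proportion by 10 percentage points and ATYR1923 Total by 5, assuming all 30 planned patients are dosed in equal arms. The number affected is unknown: an assumed 0 to 2 per arm gives 0 to 20 points, and zero is possible. The direction depends on which arm the patients are in. The four outputs are overlapping forms of one composite, so they should not be counted as four independent errors.

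The change is worth making because one case has visible leverage and the discharge reason is already collected.

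**What to change.** For the recovery and improvement endpoints only:

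1. Do not count discharge as an event when the recorded reason shows hospice or end-of-life care, transfer to another acute hospital, or leaving against advice. The exception is a WHO score ≤3 (or the required point reduction) recorded on or before discharge or at a later contact; then use the date of that score.
2. Otherwise score the patient as not recovered or not improved: a non-event in the Day 14 and Day 28 proportions, and at risk to Day 60 in the time-to-event analyses. This includes a patient who dies after hospice discharge. It must be stated explicitly, because SAP 4.2 lets the end-of-study date be the date of death. Do not censor on the day of leaving: these patients may be leaving because they are doing badly, so that censoring would be informative.
3. Rewrite the censoring sentences under time to recovery, step 3 of the oxygen-free analysis and time to improvement so that they agree with the event definition. State whether a transfer counts as a discharge, and add the discharge criterion to SAP Table 1.
4. Leave time to hospital discharge as it is.
5. Have the reasons classified by people without access to treatment codes. Report the result beside the present any-discharge rule and label it post hoc under SAP 3.2, since versions 2.0 and 3.0 of the SAP were already revised after unblinding.

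**Cost.** SAP wording, some programming and a review of about 30 discharge reasons. Recovery figures may become slightly less favourable. Recovery dates taken from later contacts (Days 7, 14, 28 and 60) are coarse and may be late. The classification works only where the recorded reason identifies why or where the patient went; the examples in step 2c describe oxygen status, not destination. Where the reason is uninformative, say so and keep the present rule for that patient.
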